1.3 Possible risks

Adverse reactions of vitamin K1: occasionally allergic reactions. Mainly occurs when the intravenous injection is too fast, more than 5mg/ minutes can cause facial flushing, sweating, bronchospasm, tachycardia,

hypotension, etc., serious allergic reactions may endanger life. Intramuscular injection can cause redness and swelling. The newborn may suffer from hyperbilirubinemia, jaundice and hemolytic anemia after the use of the product.

.1.4. Benefits

Cerebral hemorrhage is a common disease in Department of neurosurgery. It is an important measure to reduce the mortality and disability rate in the acute stage. Vitamin K1 may reduce the risk of rebleeding in patients with intracerebral hemorrhage, and the amount of brain bleeding is directly related to prognosis. Effectively reduce the amount of intracerebral hemorrhage, improve the prognosis, reduce the length of stay, reduce the time of admission to ICU and reduce the mortality.

2 Test purpose

The effectiveness and safety of vitamin K1 were mainly targeted at patients with cerebral hemorrhage (non aneurysm or vascular malformations, rupture, bleeding). To observe whether vitamin K1 can effectively avoid the increase of cerebral hemorrhage and improve the prognosis.

3 Test design

The study included spontaneous hypertensive intracerebral hemorrhage at super tentorium of cerebellum patients as the research object, to exclude cerebral aneurysms or cerebral hemorrhage, venous malformation of abnormal liver function, taking anticoagulants or antiplatelet drugs in patients. The study was divided into the experimental group and the control group, and a multicenter randomized controlled trial was conducted. In the use of a etamsylate intravenous infusion of 0.5g of patients admitted to hospital within 8 hours later, the experimental group in the incidence of cerebral hemorrhage within 2 days after the daily intravenous infusion of vitamin K1 20mg, the control group received intravenous saline, all patients were no longer use other hemostatic agents. The efficacy and safety of vitamin K1 in the early onset of cerebral hemorrhage were assessed by the observation between two groups.

A randomized, single blind, positive / placebo parallel control, multicenter, clinical trial design was used. The treatment lasted for 2 days and followed up for 6 months.

4 Subjects recruited and exited

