6.1.4 Route of administration

Basic treatment: all subjects according to the routine treatment of cerebral hemorrhage, the use of Phenol ethylamine intravenous 0.5g within 8 hours after admission, another program in accordance with the "Neurosurgery of Wang Zhongcheng", including the surgical removal of hematoma and drainage, conservative treatment, control of intracranial pressure, prevention of complications.

Test group:

Normal saline 100ml+Vitamin K1 20mg, Once a day, intravenous drip, two days in

hospital.

Control group:

Normal saline 102ml, Once a day, intravenous drip, two days in hospital.

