6.1.5 Test cycle

Medication for 2 days + followed up for 6 months.

7 Test procedure and plan

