Statistical analysis plan

1. Statistical software

Using STATA version 12.0 statistical software.

2. Special data processing

(1) Missing data: When a certain important data due to loss, miss follow-up, examination is happen, the LOCF method will be adopted to carry out the data and the secondary index will not be transferred.

(2) Outlier data: According to statistical and medical analysis, determine these data will be included or not. Sensitivity analysis was conducted for the outliers of the main targets, including two results consistent with those who did not outliers.

3. Selection of inspection level α and power of test β

(1) Difference test: With $\alpha = 0.05$ as the test standard, two-sided test was adopted, and the statistical methods, statistics and specific P values were given. $P \leq 0.05$ was considered statistically significant.

(2) Superiority test: Based on a power of 80% ($\beta = 0.2$), $\alpha = 0.025$ was conducted for the one-sided test. The difference between the groups and the 95% confidence interval of the mRS score difference to the baseline values after treatment in the experimental group and the placebo group was calculated by the least square method. If the 95% confidence interval between the two groups was greater than 0, the experimental group can be thought to be superior to the placebo group, otherwise not.

4. Statistical expression

(1) The statistical report mainly expressed in form, which was self-evident. It had the title, the heading and the number of cases, the necessary remarks and the text of statistical results and the description of data results.

(2) Descriptive statistics: The measurement data is described by mean number, standard deviation, maximum value, minimum value, 95% confidence interval, median, Q1 and Q3. The enumeration data is described by frequency (constituent

ratio), and corresponding statistics and P value are calculated.

(3) Inferential statistics: Measurement data were compared between groups by analysis of variance or K-W rank-sum test according to the distribution pattern. Enumeration data were compared between groups by R*C Chi-squared test and Fisher exact test. The ranked data was tested by CMH. The main/important therapeutic effect index will use the baseline for the covariant, considering center, operation or not after injury for analysis of covariance.

5. Specific statistical analysis content

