(1) Analysis of program implementation: a list was adopted to summarize the entry and completion of all and each central cases, and tabulate details and the data collation of those cases which are not meet the inclusion criteria, fall off, low compliance, against therapy and drug combination, interview time beyond window.

(2) Analysis the patient compliance and the drug combination during the trail.

(3) Condition of each analysis data set: Based on the analysis of the implementation of the program, determining the data imputation of each deviated test programme case. Summarize the cases of each analysis data sets, such as per-protocol set (PPS), full analysis set (FAS), safety set (SS).

(4) Baseline equalization analysis: Compare the baseline data of demographic data, vital signs and medical history related features.

(5) Analysis of curative effect index :

1) Compare the changes of mRS score to the baseline after using the drug in 2 days, followed up with 1 month and 6 months in the two groups. The main/important therapeutic effect index will use the baseline for the covariant, considering center, operation or not after injury for analysis of covariance. The covariance analysis was performed on the change of mRS score at baseline after 6 months of follow-up. The difference between the groups and the 95% confidence interval of the mRS score difference to the baseline values after treatment in the experimental group and the placebo group was calculated by the least square method. If the 95% confidence interval between the two groups was greater than 0, the experimental group can be

thought to be superior to the placebo group, otherwise not.

2) Compare the changes of cerebral hemorrhage amount to the baseline in the two groups.

3) Compare the changes of coagulation function, platelet level and GCS score to the baseline in the two groups.

4) Compare the number of days stayed in the ICU and the hospital in the two groups.

(6) Safety analysis:

Compare the incidence and classification rate of complications, adverse events and adverse reactions during the test in the two groups, and list the details of each adverse event, such as the detailed occurrence, outcome and the relationship with drugs.

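### The ANCOVA that decides 6-month mRS superiority adjusts for surgery without limiting it to surgery before randomisation, so the adjusted difference may not be the effect of assigning vitamin K1

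*SAP*

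**What the plan says.** SAP 4(3) specifies an ANCOVA for the main or important efficacy indices, with the baseline value as covariate and "considering center, operation or not after injury for analysis of covariance". SAP 5(5)1) repeats this and names the outcome: "The covariance analysis was performed on the change of mRS score at baseline after 6 months of follow-up". The decision rests on the least-squares difference: "If the 95% confidence interval between the two groups was greater than 0, the experimental group can be thought to be superior". The SAP gives no mRS ANCOVA without the operation term. Operation is also not among the baseline data to be compared in SAP 5(4), which lists demographics, vital signs and medical history.

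Protocol 6.1.4 makes surgery part of basic treatment for all subjects, "including the surgical removal of hematoma and drainage, conservative treatment, control of intracranial pressure, prevention of complications". It gives no indication, timing or expected rate. Study drug is given over two days in hospital, and Protocol 6.1.5 sets the cycle as "Medication for 2 days + followed up for 6 months". Protocol section 2 states the aim: "To observe whether vitamin K1 can effectively avoid the increase of cerebral hemorrhage and improve the prognosis".

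**The concern.** An ANCOVA covariate in a randomised comparison should be fixed before treatment can influence it. The operation term has no such limit: its window opens at the bleed and has no stated end. On the trial's own hypothesis K1 limits haematoma growth. If growth is one reason for evacuating a haematoma, then having an operation lies downstream of treatment.

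The model would then compare arms within operated and non-operated patients, two groups that treatment helped to form. There are two possible consequences:

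- **Dilution.** A real benefit acting through less growth is partly absorbed by the operation term.
- **A spurious difference.** If surgery rates differ by arm and unmeasured severity drives both surgery and mRS, operated patients in one arm are no longer comparable with operated patients in the other.

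The mRS superiority claim depends on this one adjusted difference, and its output alone would not reveal either problem.

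**Working it through.** The documents give no sample size, SD, operation rate or expected effect, so there is no plan figure to reproduce. The checks below show direction and a plausible range. **Every numerical input is an assumption.** A higher outcome is worse, so benefit is negative.

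**1. Hand calculation.** Assume that expansion occurs in 30% of controls and 20% on K1, that it worsens mRS by 1 point, and that surgery follows in 15% without expansion and 60% with it. Surgery has no effect of its own, and there is no unmeasured severity.

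- True effect: (0.20 - 0.30) × 1 = -0.100.
- Operated, control: 0.70×0.15 + 0.30×0.60 = 0.285. Operated, K1: 0.80×0.15 + 0.20×0.60 = 0.240.
- Expansion among operated: 0.18/0.285 = 0.632 v 0.12/0.240 = 0.500, difference -0.132.
- Expansion among non-operated: 0.12/0.715 = 0.168 v 0.08/0.760 = 0.105, difference -0.063.
- Least squares weights each stratum by (control share × K1 share)/(sum of the two): 0.285×0.240/0.525 = 0.130 and 0.715×0.760/1.475 = 0.368.
- Adjusted effect: -(0.132×0.130 + 0.063×0.368)/(0.130 + 0.368) = -0.081, so 81% is retained.

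If surgery itself shifts mRS by -0.3, the true effect is -0.100 + 0.045×0.3 = -0.0865 and 93% is retained. At +0.3 it is -0.1135 and 71% is retained. A simulation over 18 scenarios (surgery after expansion 40% to 80%, surgery effect -0.3 to +0.3, with and without unmeasured severity) gave 40% to 101% retained overall, and 60% to 93% at the 60% rate. The range therefore includes no loss.

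**2. Continuous model with unmeasured severity.** Assume that K1 lowers growth by 0.5 SD, that growth adds 0.4 per SD to the outcome (true effect 0.5 × 0.4 = 0.20 in size), residual SD 1, and that severity raises both surgery and outcome. The weight is how strongly post-dose growth enters the surgery decision. Each large-sample estimate uses 2,000,000 patients.

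| Weight | Operated, control v K1 | Without operation term | With operation term |
|---|---|---|---|
| 0 | 27% v 27% | -0.200 | -0.201 |
| 0.5 | 28% v 23% | -0.205 | -0.165 |
| 1 | 31% v 22% | -0.198 | -0.118 |

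Against 0.20, the loss is 1 - 0.165/0.20 = 18% at weight 0.5 and 1 - 0.118/0.20 = 41% at weight 1. At weight 1, power falls from 39% to 18% with 400 patients in total and from 67% to 33% with 800 (4,000 simulated trials each).

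**3. K1 changes growth and hence surgery, but not mRS.** Without the operation term the estimate is about 0. With it, the estimate is +0.027 at weight 0.5 and +0.036 at weight 1, a false harm. With 800 patients, rejection in that direction rises from about 2.5% to 5.0% and 7.0%.

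**4. K1 changes nothing, so surgery rates are equal.** There is no bias. Rejection stays between 2.1% and 2.8% per side, with or without the term, at 200 to 800 patients.

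**The case against.** Protocol 6.1.4 lists surgical removal beside conservative treatment, which reads equally well as a management choice made on the admission scan. In that case the operation term behaves like a baseline factor, and the weight-0 row shows no bias. This objection stands, and it limits the point to what may happen.

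A reader might infer several stronger things that the documents do not support:

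- *That operations are mostly decided after dosing and are driven by haematoma growth.* No timing, trigger or rate is stated. The entry volume of 10 to 45 ml does not imply it, because the documents give no volume threshold for surgery.
- *That adjustment removes part of any K1 effect.* The simulated range reaches 101% retained.
- *That a false effect arises whenever K1 does nothing.* It also needs surgery rates to differ by arm. The single-blind design makes it possible that knowledge of allocation influences surgery, but the documents do not say that those deciding on surgery know the allocation. If they did, dropping the term would not cure everything: a 10-point difference in surgery rates with a surgery effect of ±0.3 shifts the unadjusted estimate by 0.10 × 0.3 = 0.03 either way.
- *That the model favours K1.* The calculations show dilution and false harm. A false benefit would need the opposite pattern, with better-prognosis patients being the ones operated on.

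The bias may also be modest. Losing 60% of an effect of 0.08 to 0.12 points is 0.05 to 0.07. With an assumed SD of 1.5 to 2 and 200 to 800 patients, the standard error 2×SD/√N runs from 0.11 to 0.28. The bias is therefore below one standard error, but it is systematic and does not shrink with sample size.

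**Conclusion.** The point holds in conditional form. The SAP adjusts its deciding mRS comparison for a variable that may arise after randomisation, sets no time limit on it, and offers no analysis without it. If growth after dosing influences who is operated on, which the trial's hypothesis makes plausible, the adjusted difference is not the effect of assigning K1. Under the assumptions shown, the loss ranges from none to about 60%, and the false-direction error rate rises from 2.5% to at most 7.0% with 800 patients. There is no bias if all operations are decided before dosing, or if treatment does not change who is operated on. The documents establish neither condition, and the SAP does not plan to check them. The direction is well founded; the sizes are illustrative.

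**What to change.** In SAP 4(3) and 5(5)1), delete the operation term from the primary ANCOVA and keep the baseline value and centre. Alternatively, restrict the term to operations performed before randomisation, identified from recorded operation and randomisation dates and times. Apply the same rule to any other index analysed with this ANCOVA. Report operations after randomisation by arm, with their timing. Keep the operation-adjusted model only as a sensitivity analysis, labelled as conditioning on a variable that may follow treatment. Adding day-0 haematoma volume and admission GCS as covariates is optional.

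The first option changes only SAP wording. The second also needs the timing data. Protocol 7.5.1 already asks for the time of other treatments in the case report form, but this should be made explicit for operations. The downside is a possible small loss of precision. In the weight-0 case, where the term is harmless, leaving it out lowered simulated power from 39.6% to 39.1% with 400 patients and from 66.8% to 65.6% with 800.

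A separate matter to settle at the same time: Protocol 7.3 and section 8 schedule mRS only at 1 and 6 months, so the SAP should define the baseline mRS value that the model uses.

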1.1.1 Epidemiological of cerebral hemorrhage

Cerebral hemorrhage is a kind of acute onset, rapid change, serious disease, which accounts for about 10%-25% of cerebrovascular disease, disability rate and fatality rate were 70%-80%, 38%-43%, the recurrence rate was about 1 1.8%-11%. Hypertension and amyloid cerebrovascular disease are the main causes of primary spontaneous intracerebral hemorrhage, and hypertension is the most common risk factor for intracerebral hemorrhage. Cerebral hemorrhage not only has a serious impact on patients, but also brings heavy burden to society and family. The treatment of cerebral hemorrhage is complicated , which is one of the stroke which is proved by evidence-based medicine to be effective. Standardized treatment and effective integrated management can significantly reduce the fatality rate and improve the outcome of intracerebral hemorrhage.

Delayed cerebral hemorrhage is one of the important reasons for the aggravation of cerebral hemorrhage . The amount of hematoma in patients with intracerebral hemorrhage is closely related to the secondary injury of nerve function, which directly affects the prognosis of patients. Delayed cerebral hemorrhage is closely related to coagulation dysfunction. The prevention of delayed hemorrhage is an important part in the treatment of cerebral hemorrhage. The blood coagulation is initiated immediately after Acute intracerebral hemorrhage, and the coagulation process is divided into three stages: prothrombin complex formation, prothrombin activation, and fibrin formation. Synthesis of Coagulation factor FX, F II, F VII and F IX are dependent on vitamin K1. Vitamin K1 can cause the formation of prothrombin complex, clot solid, effectively blocking the vascular rupture, so that the amount of bleeding decreased. However, while controlling bleeding, the risk of thrombosis may be induced, and how to effectively control bleeding and avoid thrombosis is often a clinical problem.

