7.5.3 Medication and treatment are permitted

(1) The other combined diseases without affecting the curative effect and safety evaluation, can be symptomatic medication, but it must be the case report form to record the medicine general or other treatment, dosage, reason, use frequency and time etc, so as to summarize, analyze and report.

⁽²⁾The follow-up period can use cognitive rehabilitation methods, including occupational therapy, implicit memory rehabilitation, errorless learning, cognitive neuropsychological rehabilitation, rehabilitation and computer assisted cognitive rehabilitation, virtual remote control via the Internet, and the electromagnetic stimulation, should be recorded in detail in CRF.

⁽³⁾The combination drugs used for adverse events during the trial should be recorded in CRF.

8 Therapeutic evaluation standard

Main outcome measures: the amount of intracerebral hemorrhage (0d, 1D, 3D, 7D) at each time after the onset of disease.

Main outcome measures: (1) the amount of the time changes in blood coagulation, platelet levels and GCS scores after the onset (0d, 1D, 3D, 7D); (2) days in ICU; (3) the total hospitalization days; (4) complications including neurological complications, complications, blood coagulation circulatory complications after cerebral hemorrhage; (5) 1m and 6m mRS score.

9 Safety evaluation

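### The 6-month mRS superiority ANCOVA leaves out day-0 haematoma volume, an entry measurement the protocol links to prognosis, so the deciding confidence interval is probably wider than it needs to be

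*SAP*

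**What the plan says.** SAP 5(5)1) decides superiority from the least-squares difference between arms in change of mRS, and its 95% confidence interval. The time point is 6 months: "The covariance analysis was performed on the change of mRS score at baseline after 6 months of follow-up". For covariates, SAP 4(3) and 5(5)1) use the same sentence: the main or important index "will use the baseline for the covariant, considering center, operation or not after injury for analysis of covariance". That gives three terms: baseline of the index, centre, and operation.

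The protocol holds other entry data:
- **Haematoma volume.** Inclusion criterion 5 (section 4.2) requires 10 to 45 ml on imaging. The first main outcome in section 8 is "the amount of intracerebral hemorrhage (0d, 1D, 3D, 7D) at each time after the onset of disease".
- **GCS.** It is listed at admission in inclusion criterion 4 and from day 0 in section 8.
- **Age.** It is limited to 18 to 65 years in section 4.2 and recorded under section 7.1.

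On volume and prognosis, section 1.1.1 ties the amount of haematoma to secondary neurological injury, "which directly affects the prognosis of patients". Section 1.4 says "the amount of brain bleeding is directly related to prognosis". Neither document says the same of GCS or age.

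**The concern.** The case for treatment is that less bleeding means a better outcome. The model that tests outcome nevertheless does not use how much bleeding each patient had at entry. Variation in mRS that entry volume could explain therefore stays in the residual error, and the interval that decides superiority widens.

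Nothing else in the plan fills this gap. No stratification of randomisation by volume, GCS or age is described. SAP 5(4) compares baseline demographics, vital signs and medical history, but it does not name volume or GCS and leads to no adjustment.

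The three planned terms may also do less than they seem to. The only mRS assessments described are telephone scores at 1 and 6 months (protocol 7.3), so a baseline mRS may not exist. Operation is part of basic treatment (6.1.4) with no stated timing, so it may be decided after randomisation. Those are separate questions, but they make a solid entry covariate more useful.

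**Working it through.** **Inputs from the documents.** SAP 3(2) gives a one-sided α of 0.025 and power of 80%. The critical value is 1.960, the same as for a two-sided 95% interval, so test and interval agree. The 80% itself cannot be reproduced, because no sample size, effect size or SD is stated. It is taken as the starting point.

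**Assumed input.** R² is the share of the residual variance of the planned model that is explained by the added covariates. The documents give no value, so a range is shown.

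**Step 1: gain before any cost.** Residual variance is multiplied by (1 − R²), so

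power = Φ[(1.960 + 0.842)/√(1 − R²) − 1.960], and equivalent sample size = 1/(1 − R²).

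| Assumed R² | SE multiplier | Argument of Φ | Power | Equivalent extra patients |
|---|---|---|---|---|
| 0 | 1.000 | 0.842 | 80% | 0% |
| 0.05 | 0.975 | 0.914 | 82.0% | 5% |
| 0.10 | 0.949 | 0.993 | 84.0% | 11% |
| 0.20 | 0.894 | 1.172 | 87.9% | 25% |
| 0.30 | 0.837 | 1.389 | 91.8% | 43% |

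**Step 2: cost of three parameters.** Chance imbalance in q added covariates inflates the variance by about (v − 1)/(v − q − 1). Here v is the residual degrees of freedom of the planned model. With five centres assumed, v = N − 8 (intercept, treatment, baseline, operation and four centre terms). Break-even R² is 1 − 1/inflation.

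| Assumed total N | Inflation, q = 3 | Break-even R² | Power at R² = 0 | at 0.05 | at 0.10 | at 0.20 | at 0.30 |
|---|---|---|---|---|---|---|---|
| 60 | 51/48 = 1.063 | 0.059 | 77.6% | 79.6% | 81.7% | 86.0% | 90.1% |
| 100 | 91/88 = 1.034 | 0.033 | 78.7% | 80.7% | 82.7% | 86.9% | 90.9% |
| 200 | 191/188 = 1.016 | 0.016 | 79.4% | 81.4% | 83.4% | 87.4% | 91.3% |
| 300 | 291/288 = 1.010 | 0.010 | 79.6% | 81.6% | 83.6% | 87.6% | 91.5% |

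With volume alone (q = 1), break-even at N = 60 falls to 1 − 50/51 = 0.020.

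**Step 3: check on a 0 to 6 scale.** A simulation used N = 100 and five centres. Baseline mRS and operation were already in the model and correlated with volume and GCS. All effect sizes were assumed.

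| Assumed prognostic strength | Variance ratio (with / without the three) | Power without → with |
|---|---|---|
| None | 1.03 | 80% → 79% |
| Weak | 0.97 | 79% → 80% |
| Moderate | 0.85 | 72% → 80% |
| Strong | 0.74 | 65% → 78% |

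The simulation agrees with Steps 1 and 2 in direction: a small loss if the covariates carry nothing, and a useful gain if they are moderately prognostic.

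**The case against.** The strongest reply has four parts.

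1. **Validity is untouched.** This stands. A reader might infer that omitting volume biases the result or leaves an imbalance that invalidates it. With randomised arms it does neither, and the planned interval already allows for chance imbalance.
2. **The size is assumed.** This stands. A reader might take 11% to 43% more patients as the trial's loss. The documents give neither N nor R². The entry limits of 10 to 45 ml and 18 to 65 years, and the exclusion of irregular and intraventricular bleeds (4.3), restrict what the covariates can explain. The operation term may already carry part of it. In a small trial with uninformative covariates, adjustment loses a little, so the gain is not free.
3. **Only volume has support in the documents.** This stands for GCS and age, which are offered only as entry data. For volume, the protocol speaks of a relation to prognosis. It does not say that entry volume determines outcome.
4. **The data may not be ready.** This stands in part. Volume must be known to apply criterion 5. GCS is less certain: sections 4.2 and 8 place it at admission or day 0, while the flow chart (7.5) appears to tick it only at months 1 and 6. That table is damaged in the text available, so it does not show that baseline GCS is missing. No section states that day-0 values precede the first dose.

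The point does not extend to the first-listed main outcome, haematoma volume. There, adjusting for the baseline of the index already means adjusting for baseline volume.

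**Conclusion.** The mRS superiority model omits an entry measurement that the trial takes and the protocol relates to prognosis. The deciding interval is therefore likely wider than it needs to be. This is a loss of precision.

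From a nominal 80%, power would be about 82% to 92% for an assumed added R² of 0.05 to 0.30. The cost of three parameters takes off up to about 2.4 percentage points at N = 60 and 0.4 at N = 300. Adjustment pays once the added R² exceeds about 0.06 at N = 60, or 0.01 at N = 300. These figures rest on the assumed R², N and five centres, and on covariates being added to the planned model with nothing removed. They do not apply to a model that drops baseline mRS or operation.

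It is a cheap improvement that is worth making.

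**What to change.** Before unblinding, amend SAP 4(3) and 5(5)1) so that the mRS models at 1 and 6 months add these to the planned terms, each as a continuous pre-dose value:
- haematoma volume, taken from the scan used for eligibility;
- age;
- GCS at admission.

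Keep the SAP's model without the added covariates as a sensitivity analysis. Decide the handling of baseline mRS and of operation separately.

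Reconcile sections 4.2 and 8 with the flow chart on when GCS is recorded, and state that the day-0 values used as covariates precede the first dose. If day-0 GCS is not recorded, add volume and age only.

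**Cost:** a sentence in the SAP and possibly a short protocol clarification. No extra visits are needed, and no new data if day-0 GCS is confirmed. The statistical price is up to three degrees of freedom, which matters only if the trial is small and the covariates prove uninformative. The change should be pre-specified, because covariates chosen after unblinding would not be credible.

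### The SAP's only labelled superiority test needs a baseline mRS that no legible part of the protocol or SAP times or defines

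*SAP*

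**What the plan says.** SAP 3(2) sets the superiority test: 80% power, one-sided 0.025, and a 95% confidence interval for the group contrast in "the mRS score difference to the baseline values after treatment in the experimental group" and in the placebo group. Superiority follows if that interval lies above 0. No other outcome is attached to this rule.

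SAP 5(5)1) repeats the rule and fixes the time: "The covariance analysis was performed on the change of mRS score at baseline after 6 months of follow-up". The wording is rough, but read with 3(2) it means the change from baseline to 6 months. SAP 4(3) and 5(5)1) also make baseline a covariate: "The main/important therapeutic effect index will use the baseline for the covariant", together with centre and operation. SAP 5(5)1) appears to add a comparison of mRS change after the 2 days of drug.

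In the protocol, section 7.3 schedules mRS by telephone at 1 and 6 months after onset, and section 8 (second list, item 5) gives the same two times. Section 7.1 item 7 names mRS as the scale to be assessed, with no time. Section 7.2 refers to the flow chart for timing.

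**The concern.** A change score that is also adjusted for baseline uses the baseline value twice, once in the outcome and once as covariate. If that value has no stated time and no definition, the analyst must settle both after data exist. Two natural candidates, disability before the stroke and disability at admission, are different quantities, and the documents do not choose between them.

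At stake is the one analysis to which the SAP attaches a power figure, a one-sided level and a conclusion of superiority over placebo.

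**Working it through.** The documents give no sample size, effect size or standard deviation, so there is no trial figure to reproduce. The check sets the texts side by side.

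**1. mRS values needed against mRS values timed.** The 6-month superiority test needs two values per patient: baseline and 6 months. The protocol explicitly times the second only, so 1 of 2 is untimed. For all of SAP 5(5)1) the count depends on how its 2-day phrase is read:
- If it only describes the treatment period, three values are needed (baseline, 1 month, 6 months) and 1 of 3 is untimed.
- If it is a separate comparison, four are needed and 2 of 4 are untimed, since no protocol text explicitly times a 2-day mRS.

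A 2-day score follows treatment, so it cannot serve as the baseline on either reading.

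**2. The other change-from-baseline measures.** SAP 5(5)2) says "Compare the changes of cerebral hemorrhage amount to the baseline in the two groups" and 5(5)3) says "Compare the changes of coagulation function, platelet level and GCS score to the baseline in the two groups". Against protocol section 8:

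| Measure analysed as change | Times in protocol section 8 | Day-0 value stated? |
|---|---|---|
| Haemorrhage volume | 0d, 1, 3, 7 days | yes |
| Coagulation | 0d, 1, 3, 7 days | yes |
| Platelets | 0d, 1, 3, 7 days | yes |
| GCS | 0d, 1, 3, 7 days | yes |
| mRS | 1 and 6 months | no |

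The first row rests on "the amount of intracerebral hemorrhage (0d, 1D, 3D, 7D"; the next three rest on item 1 of the second list. Four of five measures have a stated day-0 value, and mRS is the exception.

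**3. Other places where a baseline mRS could appear.** SAP 5(4) describes the baseline comparison as "Compare the baseline data of demographic data, vital signs and medical history related features"; mRS is not named. In the extracted flow chart the MRS row has marks only in the two follow-up columns. The GCS row looks the same there, although section 8 requires GCS from day 0 to day 7. The extracted chart has therefore lost content and settles nothing either way.

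**4. What the change wording contributes.** Write B for baseline mRS, Y for the 6-month mRS and T for treatment. The planned model is Y − B = a + τT + βB + other terms. Adding B to both sides gives Y = a + τT + (β + 1)B + other terms. The treatment effect τ is identical, so with B as covariate the change format adds nothing to the comparison. What B can add is precision.

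**5. How much precision, for illustration only.** Assume a standardised difference of 0.5, two-sided 0.05 and 80% power. Then n per arm = 2 × (1.960 + 0.842)² × k / 0.5² = 62.8k, where k = 1 without a baseline and k = 1 − r² for ANCOVA, r being the correlation of baseline with the 6-month score. The documents give no r.
- r = 0: 63
- r = 0.2: 62.8 × 0.96 = 60.3, so 61
- r = 0.5: 62.8 × 0.75 = 47.1, so 48
- r = 0.8: 62.8 × 0.36 = 22.6, so 23

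Which state counts as baseline can therefore matter for precision if the candidate scores differ in r.

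**The case against.** The strongest reply is that an entry mRS was probably intended. Section 7.1 item 7 closes a list made up mostly of entry assessments. Section 8 lists outcomes, so its two mRS times need not be the only assessments. The flow chart, which governs timing, cannot be read reliably, and the case report form is not among the documents. This stands: a reader might infer that no baseline mRS was collected, and the documents do not show that. It does not remove the gap, because no legible text says when an entry score is taken or which state it describes.

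A second reply is that the SAP defines baseline for none of the five measures, and that section 8 counts its days from onset. That also stands. The contrast is between having and lacking a stated day-0 value, not between a defined and an undefined baseline.

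Two stronger readings are tempting:
- A reader might infer that the trial's main efficacy comparison fails. Section 8 heads two lists as main outcomes. Haemorrhage volume comes first and is unaffected, as is a direct comparison of the 1- and 6-month mRS. SAP 3(1) also provides a general difference test at 0.05, for which a "two-sided test was adopted, and the statistical methods, statistics and specific P values were given".
- A reader might infer that a late choice among baselines inflates the false-positive rate. That would need entry scores the documents do not time, so no inflation is claimed.

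**Conclusion.** The gap is real and should be fixed; confidence is moderate. From the assessments explicitly scheduled, the SAP's only labelled superiority analysis cannot be computed, because one of its two mRS values is untimed and undefined and that value is also the covariate. mRS is the only one of five change-from-baseline measures without a stated day-0 value. The apparent 2-day mRS comparison has the same lack of a timed assessment.

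This rests on the legible text. A day-0 mark in the intact flow chart would supply the time, though not the choice between pre-stroke and admission state. No effect on error rates or on the trial's power is claimed; the sample-size illustration uses assumed inputs.

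**What to change.** Before outcome data are examined, revise SAP 3(2) and 5(5)1):

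- Make the endpoint the 6-month mRS score itself, compared by ANCOVA. Leave the existing centre and operation terms as they are; whether to keep operation is a separate question.
- In place of the undefined baseline mRS, use D0 haematoma volume and D0 (admission) GCS as covariates. Protocol section 8 already times both, and 4.2 item 4 also names GCS at admission.
- Define the difference as control minus experimental adjusted mean. A higher mRS is worse, so a 95% interval wholly above 0 then means benefit. The SAP does not state the order of subtraction.
- Remove the change-from-baseline wording for mRS. Remove the 2-day mRS comparison unless a 2-day mRS is in fact collected.

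If an entry mRS was collected from all patients, instead state its timing and the state it describes in both protocol and SAP, and keep the planned ANCOVA.

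The first route changes SAP wording only and needs no new assessment; the alternative needs text in both documents. The downside of the first route is that the result is no longer expressed as a change from baseline. The scoring of deaths and the LOCF rule are separate matters, not settled here.
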